Quantitative data: We will use descriptive statistics (i.e., frequencies, means and standard deviation estimates) to describe the analytical sample. We will examine whether the implementation strategies (i.e., advisory board, use of REDCap handheld tablets, use of the PSC tool and an implementation coach) increases the number of children screened and referred to support services, compared to baseline. To do that, we will use methodology that accounts for repeated measures over time and that accounts for both within-person and across-person variation (i.e., Generalized linear mixed model (GLMM)) while controlling for clustering of patients within clinics and possible confounding by calendar time. *Our analysis will include sex as a biological variable, testing for a differential effect on outcomes by child sex.* We will report the magnitude of missing data and compare demographic and clinic characteristics and outcomes between observations with versus without missing data. In sensitivity analyses, we will perform multiple calculations (i.e., imputations) using fully conditional specification to obtain 10 complete datasets; summary estimates of intervention effects with 95% confidence limits over the 10 datasets will incorporate within- and between-dataset sampling variability.

Comparison of randomized intervention sites to non-randomized control sites

Due to the human and financial impact of COVID-19 epidemic, the randomized control periods had not implemented ACEs screening at the time of the pilot starting. We have identified two clinics that have implemented ACEs screening that are not part of the trial.

To obtain an additional non-randomized estimate of the intervention effect, we will compare:

- (1) the control periods in the randomized clinics to comparable time periods in the non-randomized clinics;
- (2) the intervention periods in the randomized clinics to comparable time periods in the non-randomized clinics.

We will use the same GLMM models as described above, with indicator variables for non-randomized vs randomized clinic, and randomized control vs intervention periods. Groups will be compared on ACEs screenings, and mental health referral rates.

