ACCORDS

ADULT AND CHILD CENTER FOR OUTCOMES
RESEARCH AND DELIVERY SCIENCE

UNIVERSITY OF COLORADO
CHILDREN'S HOSPITAL COLORADO

Supporting the Implementation of a State Policy on Screening for Adverse Childhood
Experiences (ACEs) in Federally Qualified Health Centers (FQHC).

Statistical Analysis Plan

NCT: 04916587

Date: 7.20.2024

Statistical Analysis Plan

Title of Study: Supporting the Implementation of a State Policy on Screening for Adverse Childhood Experiences (ACEs) in Federally Qualified Health Centers (FQHC)

NIMH Study ID Number: R21MH123835

Clinical Trial Number: NCT04916587

Sponsor: Study funded by the National Institute of Mental Health.

Principal Investigator: [name] [name].

Summary and research objective(s):

Screenings for Adverse Childhood Experiences (ACEs) promote early identification of toxic stress and potential trauma, allowing for intervention and possible amelioration of detrimental effects of the ACEs. The state of California enacted a 2020 fee-for-service healthcare policy, ACEs Aware, reimbursing clinics for annual ACEs screenings during well-child visits, but did not provide guidance on screening implementation. This study aims to test the effectiveness and acceptability of a multifaceted implementation strategy for implementing ACEs screenings, in partnership with a Federally Qualified Health Center (FQHC) system in California that adopted the ACEs Aware policy in August of 2020.

The proposed strategy is comprised of personnel training (e.g., Trauma-informed care), integrated technology with a customized screening scoring and aligned service referral algorithm, team-based screening workflows, ongoing care team coaching, and peer support. Significant changes to the original study protocol were needed to accommodate the negative impact that the COVID-19 pandemic had in the partner FQHC system.

Hypotheses

1. ACEs screenings

- a. Clinics using implementation strategies will have higher rates of REACH of ACEs screenings compared to their screening rates before implementing the strategies.
- b. Clinics using implementation strategies will have higher rates of REACH of ACEs screenings than clinics screening for ACEs and as part of the state funded CALQIC project, without the implementation strategies.

- c. Exploratory: Are there any differences between in the effectiveness of the implementation strategies in different sub-groups (such as race, ethnicity, age and gender)?

2. Referrals to mental health services

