- a. Clinics using implementation strategies will have higher rates of mental health referrals compared to their referral rates before implementing the strategies.
- b. Clinics using implementation strategies will have higher rates of mental health referrals than clinics screening for ACEs and as part of the state funded CALQIC project, without the implementation strategies.
- c. Among children screened, ACEs screenings indicating medium and high risk will lead to mental health referrals at higher rates than screenings indicating low risk.
- d. Exploratory: Are there any differences between in the effect of the implementation strategies on referrals in different sub-groups (such as race, ethnicity, age and gender)?

[figure not shown]
3. Implementation outcomes

- a. Perceive feasibility, acceptability, and usefulness of the intervention will be sufficiently high (see Table 1).

Study design:

Changes to the original study design were needed to accommodate the negative impact that the COVID-19 pandemic had in the partner FQHC system. We conducted a stepped-wedge design (SWD) trial with three sites, with data collection divided into 7 10-week intervals. Study sites remained in the intervention phase for multiple intervals to allow additional data to be collected. In addition to the 3 study sites, 2 additional sites from the same health system served as comparison sites, implementing ACEs screenings without the support of the implementation strategies. See Figure 1 for the SWD schedule.

Figure 1. Stepped-wedge schedule for the ACEs pilot study.

Study sites and patient eligibility:

The study statistician originally selected five clinics from a pool of 16 clinics providing family medicine, pediatric, or primary care for children ages 0 to 5 years old and across five regions to maximize variation (e.g., clinic characteristics such as resources and size). Clinics were located in urban, suburban, rural, and frontier communities. The study PI and FQHC champions invited the identified clinics via email to an informational video session to introduce the study and provided study informational materials to the clinic manager.

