Once the pilot study started, two randomly selected clinics were not able to participate - one clinic closed and one clinic lost their pediatrician leading ACEs screenings. Due to extremely high staff turnover at the clinics and among FQHC leadership, additional clinics selected were not able to participate in this research study. Thus, from the three clinics that finished the stepped wedge schedule, one was randomly selected and two clinics joined based on their capacity to participate in a research study at that time.

Eligible children were those aged 0-5, on public insurance, attending a wellness visit with the participating clinician.

Data sources:

Data for the primary outcomes, including reach of ACEs screenings and mental health referral rates, was obtained via the electronic medical record (EMR) at the partner health system. Additional data for secondary analyses was collected using REDCap among intervention patients only, including the PSC scores and ACEs screening results. See Figures 2 and 3 for the Consort tables.

Figure 2. CONSORT table for the study pilot study – Electronic Medical Records Data.

[figure not shown]

Figure 3. CONSORT table for sub-sample of data – REDCap system.

[figure not shown]

Table 1. Description of measures

Measure	Description/psychometrics	Source
ACEs Screening		
PEARLS¹ screening (ages 0-11)	Caregiver-reported tool (17-items) designed to identify exposure to childhood adversity and stress factors that may lead to toxic stress and negative health outcomes. Number of endorsed events are summed up (0-4+) to identify risk level for toxic stress and potential symptomatology. English/Spanish	Caregiver
ACEs associated health conditions²	State-sponsored list with 25 ACEs associated health conditions for children ages 0 – 5. ² Physical conditions include asthma, allergies, unexplained somatic symptoms such as headaches. Mental health related conditions (over 10) include aggression, depression, ADHD, and anxiety	EMR system

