Descriptive statistics will be used to describe the sample of children and clinics. The sample will be described using counts and percentages, and treatment groups will be compared using chi-squared tests. We will calculate risk differences with confidence limits for each of our three groups of interest- the study clinics during the control period, study clinics during the intervention period, and the control clinics. For subgroup analyses exploring differences by child demographics, we will calculate risk differences within those subgroups (age, gender, race, and ethnicity).

The reach variable (proportions screened) will be analyzed using binary regression (a generalized linear model, specifying a binomially-distributed dependent variable and identity link function). Modified Poisson regression with robust variance estimation¹⁴ will be used to analyze mental health referrals to estimate adjusted risk differences. Both models will compare the intervention and control arms as the primary independent variable of interest. Possible covariates will include child's sex, age category (<18 months, 18-60 months), child's race (white, black, other/unknown), child's ethnicity (Latino, not Latino, unknown/not reported), language of preference, and study site; covariates will be included in their adjustment changes the intervention regression coefficient by more than 15%.

Models comparing the intervention and comparison clinics will be adjusted for the child's race and for the study site. Missingness in demographic data will be handled by including an 'unknown or not reported' category. Survey data will be analyzed using aggregated intra-class correlations (ICC) to assess within-group agreement, whether clinic care teams shared perceptions of readiness for change during the preparation phase, and implementation climate and leadership. ICC is the variance proportion attributed to care teams.¹⁵ Higher scores in these measures reflect higher organizational support for the translation of a new clinical practice into practice.¹⁶ An agreement of 0.70 or higher reflects an organizational measure.¹⁷

References

1. National Pediatric Practice Community. PEARLS FAQs. Accessed August 14, 2019. <https://nppcaces.org/faqs/>
2. Aware A. ACES Screening Clinical Workflows. Accessed June 15, 2020. <https://www.acesaware.org/wp-content/uploads/2019/12/ACE-Clinical-Workflows-Algorithms-and-ACE-Associated-Health-Conditions.pdf>

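### The SAP's comparison of 3 study clinics with 2 comparison clinics (H1b, H2b) has no between-clinic variance in its confidence limits or models, and its study-site adjustment is aliased with group.

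*SAP*

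**What the plan says.** Under Hypotheses, the SAP states for 1b: "Clinics using implementation strategies will have higher rates of REACH of ACEs screenings than clinics screening for ACEs", and for 2b: "Clinics using implementation strategies will have higher rates of mental health referrals than clinics screening for ACEs". The Data sources section treats reach and mental health referrals as the primary outcomes. The Study design section gives the number of clinics: "In addition to the 3 study sites, 2 additional sites from the same health system served as comparison sites". Of the three study clinics, "one was randomly selected and two clinics joined based on their capacity to participate in a research study at that time" (Study sites and patient eligibility).

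The Statistical analysis section then lists, for these outcomes:

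- risk differences: "We will calculate risk differences with confidence limits for each of our three groups of interest", the groups being study clinics in their control period, study clinics in their intervention period, and the comparison clinics;
- for reach, a binomial GLM with identity link;
- for referrals, modified Poisson regression with robust variance, with no clustering unit named;
- for models comparing intervention with comparison clinics, adjustment for child's race and study site.

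The section names no random clinic effect, GEE, clinic-clustered variance or small-cluster correction for reach or referrals. It uses intraclass correlation only for the staff surveys.

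Protocol section V.c (Data Analysis) differs. It specifies a GLMM "controlling for clustering of patients within clinics and possible confounding by calendar time" and says the same GLMM will serve the comparison with the non-randomized clinics. The SAP does not explain the change.

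**The concern.** The strategy is delivered to whole clinics, so in H1b and H2b it varies only between clinics. Any ordinary difference between clinics in screening or referral practice goes straight into the estimated effect. An interval built only from child-level binomial variation leaves that source out and is too narrow. Enrolling more children per clinic makes this worse, because the child-level standard error shrinks while the between-clinic component stays the same.

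Between-clinic variation is hard to dismiss here. The SAP says the initial selection of clinics aimed to maximize variation in characteristics such as resources and size, and two of the three study clinics joined because they had capacity to take part. At stake is the inference on two stated hypotheses about primary outcomes. This point is about the error bars and the estimability of the contrast, not about bias from non-random selection or calendar trend.

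**Working it through.** The documents state no sample size, power, alpha or ICC for H1b or H2b, so there is no figure of the plan's own to reproduce.

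**Inputs.** From the SAP: 3 and 2 clinics (Study design), a current referral rate of 3.8% and expected reach of 80–92%, midpoint 86% (Table 1). Assumed: a two-sided 5% test, equal clinic sizes of m = 90 to 300 children, and ICC 0.001 to 0.05. The EMR denominators are in figures not shown. The only child count in the text is the Protocol's 450 children kept in REDCap. 450/5 = 90 gives a rough lower anchor, but it is not an EMR denominator.

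**Step 1: error rate of a child-level test with no strategy effect.** Design effect DE = 1 + (m − 1) × ICC. True type I error = 2 × [1 − Φ(1.96/√DE)]. For example, m = 300 and ICC 0.01 give DE = 1 + 299 × 0.01 = 3.99, 1.96/√3.99 = 0.981, and an error of 33%.

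| ICC | DE, m = 90 | Type I, m = 90 | DE, m = 300 | Type I, m = 300 |
|---|---|---|---|---|
| 0.001 | 1.089 | 6% | 1.299 | 9% |
| 0.005 | 1.445 | 10% | 2.495 | 21% |
| 0.01 | 1.89 | 15% | 3.99 | 33% |
| 0.05 | 5.45 | 40% | 15.95 | 62% |

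A beta-binomial simulation of 3 against 2 clinics (40,000 runs per setting, event rates 3.8% and 86%) agreed to within about one percentage point, reaching 22% at ICC 0.005 and 63% at ICC 0.05. These rates describe the unadjusted child-level risk difference.

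**Step 2: what these ICCs mean.** Between-clinic SD = √[ICC × p(1 − p)]. At ICC 0.01 this is √(0.01 × 0.86 × 0.14) = 3.5 points for reach and √(0.01 × 0.038 × 0.962) = 1.9 points for referrals.

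**Step 3: study-site adjustment.** An intercept, a group indicator and four site indicators make 6 columns. The group indicator is an exact linear combination of the intercept and site indicators, so the rank is 5. Adding the study clinics' control periods gives 7 columns and rank 6. The within-clinic contrast can then be estimated, but the contrast with the comparison clinics still cannot. If software drops a site column to proceed, the estimate depends on which clinic was dropped, and its standard error is still child-level.

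**Step 4: clustering the robust variance on clinic.** With five clinics and a normal reference, simulated type I error was 19–25%.

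**Step 5: clinic-level analysis.** A t-test on the five clinic proportions has 5 − 2 = 3 degrees of freedom and critical value 3.18. Its simulated type I error was 4.2–5.5%. The 95% half-width is 3.18 × √(1/3 + 1/2) = 2.9 times the SD of the observed clinic proportions: 14.5 points for an SD of 5 points, 29 points for an SD of 10.

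**The case against.** The best defence has five parts.

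- **The models do mention clinic.** The intervention-versus-comparison models are adjusted for study site, so they do not simply ignore it. That is true, but Step 3 shows that this term cannot supply between-clinic variance and makes the contrast non-estimable.
- **The robust variance may be clustered.** The SAP does not rule this out. Step 4 shows it would still be anti-conservative with five clinics.
- **The chi-squared sentence.** The SAP's "treatment groups will be compared using chi-squared tests" shares a sentence with the description of the sample and most naturally concerns sample characteristics. This stands, and the point does not rely on it.
- **The ICC may be tiny.** At 0.001 the error rate is only 6–9%. This stands as a limit on the size of the problem.
- **Status.** The trial is a pilot, the Protocol calls this an additional non-randomized estimate, and the SAP states no alpha. That supports presenting H1b and H2b as estimates. It does not justify limits that omit the main source of variation.

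A reader might also draw three stronger conclusions, which the documents do not support.

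- *Chance clinic differences will be reported as significant.* The calculation gives a risk that depends on an assumed ICC and assumed clinic sizes. At ICC 0.01 most null analyses would still not be significant.
- *The effective sample size is five.* Five clinics limit the degrees of freedom. The effective number of children, 5m/DE, is 750/2.49 ≈ 301 for m = 150 at ICC 0.01 and 1500/15.95 ≈ 94 for m = 300 at ICC 0.05.
- *The design cannot reach the 5% level.* Three against two clinics allow 10 labellings, so an exact permutation test has a minimum one-sided p of 0.10. That floor belongs to that test only. A t-test on 3 degrees of freedom can reach 5%, with low power and a normality assumption resting on five values.

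**Conclusion.** The plan is wrong as written for H1b and H2b. No SAP method for this contrast carries between-clinic variance, the study-site term is aliased with group, and the SAP drops without explanation the clinic-clustered GLMM that the Protocol specifies for the same comparison. With 90–300 equally sized clinics' worth of children per site assumed, type I error at a nominal 5% is about 6–9% at ICC 0.001, 10–22% at 0.005, 15–33% at 0.01 and 40–63% at 0.05. Neither the ICC nor the clinic sizes are in the documents, so the supported conclusion is that false-positive risk may be well above 5%, not that any particular rate applies.

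H1a and H2a are within-clinic contrasts and less exposed. For them there is a conditional question. Reach is defined on visits over seven 10-week intervals and no de-duplication rule is stated, so some children may contribute more than one visit. The documents give no count of repeats.

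**What to change.** In the SAP's Statistical analysis section:

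1. For H1b and H2b, remove the study-site fixed effect.
2. Report the five clinic-level proportions over comparable periods, and the difference between the group means with a t interval on 3 degrees of freedom. If race adjustment is to be kept, use the Protocol's GLMM with a random clinic effect and a small-sample degrees-of-freedom correction instead.
3. Label H1b and H2b as estimates with low power, not confirmatory tests.
4. Reconcile this section with Protocol section V.c, and explain any remaining departure from the GLMM.
5. State whether a child can contribute more than one visit. If so, account for repeat visits in the variance for H1a and H2a.

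The cost is SAP wording and a short re-analysis. Intervals will be wider: at the between-clinic SDs in Step 2, the clinic-level half-width would be at least about 2.9 × 3.5 ≈ 10 points for reach and 2.9 × 1.9 ≈ 5.5 points for referrals, before child-level sampling variation is added. The clinic-level version also loses the race adjustment.

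### Subgroup risk differences for race and ethnicity are planned without clinic stratification, so a difference between the three clinics can pass for, or hide, a difference between groups

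*SAP*

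**What the plan says.** SAP hypothesis 1c asks: "Are there any differences between in the effectiveness of the implementation strategies in different sub-groups", naming race, ethnicity, age and gender as examples. Hypothesis 2d asks the same about referrals. Both are labelled exploratory.

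The method is one sentence in the descriptive paragraph of the SAP's Statistical analysis section: "For subgroup analyses exploring differences by child demographics, we will calculate risk differences within those subgroups (age, gender, race, and ethnicity". It names no clinic term, calendar-time term, interaction or between-group test.

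Adjustment appears only afterwards, for the main models. Modified Poisson regression "will be used to analyze mental health referrals to estimate adjusted risk differences". Study site is on the list of possible covariates for both outcomes, subject to a change-in-coefficient rule: "covariates will be included in their adjustment changes the intervention regression coefficient by more than 15" per cent. Race and site are fixed adjustments only for one comparison: "Models comparing the intervention and comparison clinics will be adjusted for the" child's race and the site. None of this is said to apply to the subgroups.

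The design is described as follows: "We conducted a stepped-wedge design (SWD) trial with three sites, with data collection divided into 7 10-week intervals". Protocol section V.c (Data Analysis) plans a mixed model that accounts for clinic clustering and calendar time. It plans a differential-effect test for child sex only.

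**The concern.** A risk difference pooled over clinics compares one weighted mean of clinic rates with another, and the weights depend on where that subgroup's visits took place. In a stepped wedge the clinics also contribute unequal control and intervention time. Two groups that gain equally within every clinic can therefore show different pooled risk differences. With only three clinics, such imbalances cannot be expected to average out.

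The strategy is delivered clinic by clinic, through coaching, screeners and tablets, so uneven effects are plausible. The Protocol's Justification warns that screening campaigns may worsen disparities, and it says the results will inform clinical partners and state policy leaders. Those readers would act differently on a finding that one clinic delivered poorly than on a finding that the strategy works less well in one racial or ethnic group.

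**Working it through.** The documents give no subgroup figure, sample size or clinic mix, so there is no planned figure to reproduce. The check is expected-value arithmetic.

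**From the documents:** three study clinics and seven intervals (SAP, Study design); expected reach of 80% to 92% and a current referral rate of 3.8% (SAP, Table 1).

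**Assumed:**
- Control intervals number 1, 2 and 3, so intervention intervals number 6, 5 and 4 (Figure 1 could not be read).
- Visit volume per interval is equal across clinics.
- Control reach is 1% everywhere. Protocol step 4.9.2 says the control clinics had not implemented screening when the pilot started.
- Group A makes up 60/50/40% or 70/50/30% of visits in the three clinics; group B makes up the rest.
- Within each clinic both groups have the same rates, so the true within-clinic contrast is zero.

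**Formula.** For group g, RD = Σ(n1·p1)/Σn1 − Σ(n0·p0)/Σn0. Here n1 is the group's share times intervention intervals, and n0 is its share times control intervals. When the control rate is the same in all clinics, it cancels from the A-minus-B contrast.

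**Weights n1.**
- Mix 70/50/30%: A 4.2, 2.5, 1.2 (sum 7.9); B 1.8, 2.5, 2.8 (sum 7.1).
- Mix 60/50/40%: A 3.6, 2.5, 1.6 (sum 7.7); B 2.4, 2.5, 2.4 (sum 7.3).

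**Pooled contrasts.** The reach rows show mean intervention reach (%). The referral rows show the mean effect in points over the 3.8% base.

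| Clinic values | Mix | A | B | A − B |
|---|---|---|---|---|
| Reach 92/86/80% | 70/50/30 | 697.4/7.9 = 88.3 | 604.6/7.1 = 85.2 | 3.1 |
| Reach 92/86/80% | 60/50/40 | 674.2/7.7 = 87.6 | 627.8/7.3 = 86.0 | 1.6 |
| Reach 70/55/40% | 70/50/30 | 479.5/7.9 = 60.7 | 375.5/7.1 = 52.9 | 7.8 |
| Reach 70/55/40% | 60/50/40 | 453.5/7.7 = 58.9 | 401.5/7.3 = 55.0 | 3.9 |
| Referral +12/+6/0 | 70/50/30 | 65.4/7.9 = 8.3 | 36.6/7.1 = 5.2 | 3.1 |
| Referral +12/+6/0 | 60/50/40 | 58.2/7.7 = 7.6 | 43.8/7.3 = 6.0 | 1.6 |

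**Unequal baselines, equal effects.** Take +40 points in every clinic, baselines of 10/30/50%, and mix 70/50/30%.
- A: 493/7.9 − 82/2.6 = 62.4 − 31.5 = 30.9.
- B: 517/7.1 − 138/3.4 = 72.8 − 40.6 = 32.2.
- The contrast is −1.4 from unrounded values, and both estimates fall short of 40.

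**Does a site main effect cure it?** Fitted within each subgroup, it weights each clinic's effect by n0·n1/(n0+n1), which is the group's share times 6/7, 10/7 or 12/7. Take reach 70/55/40% (effects 69/54/39 points) and mix 70/50/30%.
- A: weights 0.600, 0.714, 0.514, giving 54.7.
- B: weights 0.257, 0.714, 1.200, giving 47.5.
- So 7.2 of the 7.8 points remain. A single model with common site terms and an intervention-by-subgroup term leaves 6.8.

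Site terms do remove the unequal-baseline artefact. They do not remove the one caused by unequal effects.

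**Within-clinic version.** Averaged with equal clinic weights, both groups give (69 + 54 + 39)/3 = 54.0, and the contrast is 0. In simulation with 60 visits per clinic-interval, the standard deviation of this contrast changes by about 12% at most.

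**When nothing happens.** The pooled contrast is zero if the mix is the same in every clinic. It is also zero if effects and baselines are both equal across clinics.

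**The case against.** The strongest objection concerns what is being estimated. Hypothesis 1c does not say within clinic. If children of one group mostly attend a clinic where the strategy fails, that group did benefit less, and the pooled risk difference records this. That stands. The pooled figure is legitimate and should stay; what it cannot show is whether the cause is the clinic or the group.

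A reader might infer that a false racial disparity will be reported. The documents do not support that: they never call the risk differences crude or pooled, and they give neither clinic mix nor clinic-level effects.

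The SAP's statements on the clinics do not fill the gap. "Clinics were located in urban, suburban, rural, and frontier communities" comes from the account of the original selection, which sought variety in characteristics such as resources and size. Of the three clinics that finished, one was randomly selected and two joined on capacity. The phrase "Due to extremely high staff turnover at the clinics and among FQHC leadership" explains why further selected clinics could not take part; it does not show that reach differed among those that finished.

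A reader might also quote high false-positive rates. With 60 visits per clinic-interval, reach 70/55/40% and mix 70/50/30%, a test between subgroups rejects in about 61% of simulated trials. No such test is in the SAP, and that reach lies below its own expectation. At 80% to 92% reach the rate is roughly 10% to 24%.

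Finally, the analysis is exploratory, and the mechanism has little force for age and gender unless their mix also varies by clinic. All of this limits the size and certainty of the point. It does not supply the missing specification.

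**Conclusion.** The point holds in conditional form, for race and ethnicity. The SAP names no clinic stratification for hypotheses 1c and 2d. Read naturally, its subgroup risk differences cannot separate a clinic difference from a group difference.

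Under the assumed mixes, the artefact is about 2 to 3 points at the SAP's expected reach and about 4 to 8 points at reach of 70/55/40%. For referrals it is about 3 points at the stronger mix. Reversing the mix reverses the direction, so a real difference can also be masked. These sizes rest on assumed mixes, effects, volumes and crossover times. They show what could happen and do not predict the trial's result. An exploratory label lowers the stakes but does not make the pooled figure interpretable as a subgroup effect.

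**What to change.** Add one paragraph to the SAP, for race and ethnicity in the study clinics:

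- Tabulate subgroup by clinic and by control or intervention period.
- Keep the pooled subgroup risk differences. Beside them, report risk differences calculated within each clinic and averaged with the same pre-stated clinic weights for every subgroup. A model with intervention-by-site terms beside the intervention-by-subgroup term, and calendar time as in Protocol section V.c, is an alternative. Site as a main effect only is not enough.
- State in advance a minimum cell count, and what happens to a clinic that falls below it, so that dropping a clinic is not a post hoc choice.
- Interpret a difference as a subgroup effect only if it is also seen within clinics.
- Label subgroup contrasts with the comparison clinics descriptive, since clinic cannot be stratified out there.

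No new data are needed: site, race and ethnicity are already planned covariates. The cost is slightly wider intervals and some sparse cells, chiefly for referrals. With 60 visits per clinic-interval, the smallest control cell at a 30% share and one control interval is 60 × 1 × 0.30 = 18 visits. At 3.8% that is about 0.7 expected referrals. For referrals, the within-clinic figures may therefore support little more than a description.
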